18.0 APPENDICES

Appendix A: Performance Status

Zubrod (ECOG) Performance Scale

POINT	DESCRIPTION
0	Fully active, able to carry on all pre-disease performance without restriction.
1	Restricted in physically strenuous activity but ambulatory and able to carry out work of a light or sedentary nature, e.g., light housework, office work.
2	Ambulatory and capable of self-care but unable to carry out any work activities; up and about more than 50% of waking hours
3	Capable of limited self-care, confined to bed or chair more than 50% of waking hours.
4	Completely disabled; cannot carry on any self-care; totally confined to bed or chair.

Appendix B: List of prohibited medications during study drug treatment⁵

Category	Drug Name
Strong CYP3A inhibitors	Boceprevir, clarithromycin, cobicistat, conivaptan, elvitegravir, indinavir, itraconazole, ketoconazole, lopinavir, mibefradil, nefazodone, nelfinavir, posaconazole, ritonavir, saquinavir, telaprevir, telithromycin, tipranavir, troleandomycin, voriconazole
Strong CYP3A inducers	Avasimibe ³ , carbamazepine, mitotane, phenobarbital, phenytoin, rifabutin, rifampin (rifampicin) ³ , St. John's wort (hypericum perforatum) ³
Medications with a known risk for QT prolongation ⁴	Amiodarone, arsenic trioxide, astemizole, azithromycin, bepridil, chloroquine, chlorpromazine, cisapride, citalopram, clarithromycin, disopyramide, dofetilide, domperidone, droperidol, erythromycin, flecainide, halofantrine, haloperidol, ibutilide, levomethadyl, mesoridazine, methadone, moxifloxacin, pentamidine, pimozone, probucol, procainamide, quinidine, sotalol, sparfloxacin, terfenadine, thioridazine, vavdetanib
CYP3A substrates with NTI ¹	Alfentanil, astemizole, cisapride, cyclosporine, diergotamine (dihydroergotamine), ergotamine, fentanyl, pimozone, quinidine, sirolimus, tacrolimus, terfenadine
Other investigational and antineoplastic therapies	Other investigational therapies must not be used while the patient is on the study. Anticancer therapy (chemotherapy, biologic or radiation therapy, and surgery) other than the study treatments must not be given to patients while the patient is on the study medication. If such agents are required for a patient then the patient must be discontinued from the study drug.
Herbal preparations/medications	Herbal preparations/medications are prohibited throughout the study. These herbal medications include, but are not limited to: St. John's wort, Kava, ephedra (ma huang), ginkgo biloba, black cohosh, dehydroepiandrosterone (DHEA), yohimbe, saw palmetto, and ginseng. Patients should stop using these herbal medications 7 days prior to first dose of study drug.
¹ NTI = narrow therapeutic index drugs whose exposure-response indicates that increases in their exposure levels by the concomitant use of potent inhibitors may lead to serious safety concerns (e.g., Torsades de Pointes). ² Herbal product ³ P-gp inducer ⁴ Source: www.crediblemeds.org ⁵ Topical preparations are allowed	

Appendix C: List of medications to be used with caution during study drug treatment

Category	Drug Name
Moderate CYP3A4/5 inhibitors	Amprenavir, aprepitant, atazanavir, casopitant, cimetidine, ciprofloxacin, darunavir, diltiazem, dronedarone, fluconazole, fosamprenavir, grapefruit juice (citrus paradisi fruit juice), imatinib, Schisandra sphenanthera ¹ , tofisopam, verapamil
Moderate CYP3A4/5 inducers	Bosentan, efavirenz, etravirine, genistein, modafinil, nafcillin, talviraline, thioridazine
Sensitive CYP3A4/5 substrates ¹	Alpha-dihydroergocryptine, aplaviroc, aprepitant, atorvastatin, brecanavir, brotizolam, budesonide, buspirone, capravirine, casopitant, , darifenacin, darunavir, dasatinib, dronedarone, ebastine, eletriptan, eplerenone, everolimus, felodipine, fluticasone, , lovastatin, lumefantrine, lurasidone, maraviroc, midazolam, neratinib, nisoldipine, perospirone, quetiapine, ridaforolimus, , sildenafil, simvastatin, , ticagrelor, , tolvaptan, triazolam, vardenafil, vicriviroc
Strong BSEP inhibitors	Bosentan, fusidate, glibenclamide, lovastatin, , sulindac, troglitazone (TGZ- sulfate)
Mate1 and OCT2 substrates ³	Acyclovir, amantadine, amiloride, cephalixin, cephradine, cimetidine, famotidine, fexofenadine, memantine, metformin (also a substrate for OCT1, MATE1, and MATE2K), pindolol, procainamide, ranitidine, and varenicline
BCRP substrates	Daunorubicin doxorubicin, rosuvastatin, sulfasalazine, topotecan
Medications that carry a possible risk for QT prolongation	Alfuzosin, amantadine, atazanavir, chloral hydrate, clozapine, dolasetron, dronedarone, eribulin, escitalopram, famotidine, felbamate, fingolimod, foscarnet, fosphenytoin, gatifloxacin, gemifloxacin, granisetron, iloperidone, indapamide, isradipine, lapatinib, levofloxacin, lithium, moexipril, nicardipine, nilotinib, octreotide, ofloxacin, ondansetron, oxytocin, paliperidone, pasireotide, quetiapine, ranolazine, risperidone, roxithromycin, sertindole, sunitinib, tacrolimus, tamoxifen, telithromycin, tizanidine, vardenafil, venlafaxine, voriconazole, ziprasidone

¹ Sensitive substrates: Drugs whose plasma AUC values have been shown to increase 5-fold or higher when co-administered with a potent inhibitor.

² Source: www.crediblemeds.org

³ Source: FDA Draft Guidance for Industry, Drug Interaction Studies – Study Design, Data Analysis, and implications for Dosing and Labeling (February 2012) and Yonezawa and Inui (2011) Importance of the multidrug and toxin extrusion MATE/SLC47A family to pharmacokinetics, pharmacodynamics/toxicodynamics and pharmacogenomics. Br J Pharmacology 164:1817-25

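### Five drugs are prohibited in Appendix B and allowed with caution in Appendix C with no rule on which list governs, and Appendix C also lists grapefruit juice, which Section 4.1.1 forbids

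*Combined protocol and SAP*

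**What the plan says.** Section 8.4 prohibits the Appendix B drugs during study treatment. The only exception in Appendix B itself is its footnote 5: "Topical preparations are allowed". Section 8.4 separately allows herbals or supplements that the PI approves. Section 8.3 covers Appendix C: those drugs are to be kept out of use where possible but, if one has to be given, it may be given with caution, and an interruption of ribociclib should be considered if the need is short.

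Appendix B names the five drugs in three rows:

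- Strong CYP3A inhibitors: "telaprevir, telithromycin, tipranavir, troleandomycin, voriconazole"
- Known QT risk: "probucol, procainamide, quinidine, sotalol, sparfloxacin, terfenadine, thioridazine, vavdetanib"
- Narrow-index CYP3A substrates: "sirolimus, tacrolimus, terfenadine"

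Appendix C names the same five in three rows of its own:

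- Possible QT risk: "sunitinib, tacrolimus, tamoxifen, telithromycin, tizanidine, vardenafil, venlafaxine, voriconazole, ziprasidone"
- Moderate CYP3A4/5 inducers: "modafinil, nafcillin, talviraline, thioridazine"
- MATE1 and OCT2 substrates: "pindolol, procainamide, ranitidine, and varenicline"

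Its row of moderate CYP3A4/5 inhibitors also contains "grapefruit juice (citrus paradisi fruit juice". Section 4.1.1 requires subjects to avoid grapefruit and its juice for the whole study, exclusion 3.2.21 places grapefruit with the strong inducers or inhibitors, and the pill diary in Appendix F tells the participant not to take it.

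**The concern.** For each of the five drugs, one section gives an absolute bar and another a conditional permission. Someone who looks the drug up only in Appendix C would not learn that it is barred.

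The subject matter makes this more than untidiness. Section 1.5 says that ribociclib is eliminated mainly through CYP3A4, counts QT prolongation among its main adverse reactions, and warns that strong CYP3A4 inhibitors may amplify its toxicities. Section 4.5.5 sends sites back to the concomitant medications, for both CYP3A4 inhibition and QT risk, when QT is prolonged. Two of the five are on the protocol's own strong-inhibitor list and two on its known-QT list.

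There is also a possible data consequence. The calendar footnotes (5.0 note J, 5.1 note G) say that only prohibited concomitant medications go into the CRF. A site relying on Appendix C could leave one of these drugs out, although Section 8.2 still requires it in the patient record.

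**Working it through.** There is no planned figure to reproduce; the check compares the two tables by name and then looks for a rule that settles the overlap.

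**Appendix B, four drug-class rows.** Strong inhibitors 20, strong inducers 8, known QT 33, narrow-index substrates 12: 20 + 8 + 33 + 12 = 73 entries. Six names occur twice (clarithromycin, astemizole, cisapride, pimozone, quinidine, terfenadine), leaving 73 − 6 = **67** distinct names. Adding the herbal row (8 new names, since St. John's wort is already counted) and counting the bracketed synonym dihydroergotamine separately gives 67 + 8 + 1 = 76. The overlap is the same on either count.

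**Appendix C, seven rows.** Moderate inhibitors 16, moderate inducers 8, sensitive substrates 37, BSEP inhibitors 6, MATE1/OCT2 substrates 14, BCRP substrates 5, possible QT 46: 132 entries. Removing 13 repeats leaves **119** distinct names.

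**Names in both:** exactly 5. 5/119 = 4.2% of Appendix C; 5/67 = 7.5% of the Appendix B drug-class names.

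| Drug | Appendix B row (8.4: prohibited) | Appendix C row (8.3: caution) |
|---|---|---|
| Voriconazole | Strong CYP3A inhibitor | Possible QT risk |
| Telithromycin | Strong CYP3A inhibitor | Possible QT risk |
| Tacrolimus | Narrow-index CYP3A substrate | Possible QT risk |
| Thioridazine | Known QT risk | Moderate CYP3A4/5 inducer |
| Procainamide | Known QT risk | MATE1/OCT2 substrate |

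Each drug belongs to one class named in 8.4 and another named in 8.3, so the class headings alone do not say which status applies. The blank entries in Appendix C are in the sensitive-substrate and BSEP rows; the five overlaps are in other, legible rows, so lost text does not explain them.

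**Grapefruit juice.** It is not named in the Appendix B table, so it is outside the count of five. Its conflict is with 4.1.1, 3.2.21 and the pill diary. Entries to remove: 5 + 1 = 6.

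**Search for a rule of precedence.** The closest text is in Appendix D, which permits necessary medication unless it is specifically prohibited. It does not address a drug on both lists, and the lists it points forward to are not in Appendix D; Appendices B and C come before it. Sections 3.2.21, 4.1.1, 8.3 and 8.4 contain no such rule.

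**The case against.** The strongest reply is that the right reading is not really in doubt. Section 8.4 is unconditional, Section 8.3 is headed as therapy that is permitted, and Appendix D makes its general permission yield to a specific prohibition. A strong CYP3A inhibitor does not stop being one because it also carries a possible QT risk. Tables sorted by mechanism repeat names routinely, as both of these do internally, so the overlap looks like residue from merging lists.

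There are safeguards too. Patients must tell the site about new medications, medications are reviewed at each visit, and the calendar schedules ECGs on Day 1 of Cycles 2-6. Sections 8.3 and 8.4 and Appendix D call the lists a guide, and Appendix D refers questions to the medical monitor or the PI. Exclusion 3.2.21 covers these classes at entry. For grapefruit, every participant-facing instruction agrees.

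Most of this stands as a limit on the risk. It does not remove the conflict. That the prohibition wins is an inference the reader has to make, and a person who finds the drug only in Appendix C has no prompt to make it or to ask. Calling a list a guide excuses gaps, not two statuses for one drug. Entry screening does not cover an antifungal or antibiotic started during treatment, and with scheduled ECGs only at the start of a cycle, a mid-cycle start could go weeks without one.

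It is also fair to say that the percentages measure neither clinical risk nor the full extent of the inconsistency. Appendix C also names anticancer agents, and a herbal product (Schisandra), that Appendix B bars by category.

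**Conclusion.** The point holds. Five drugs carry contradictory instructions, and grapefruit juice is listed for cautious use against an explicit ban elsewhere. This is an inconsistency in an operative safety rule, worth correcting but of modest severity. What remains at risk is mainly a drug started during treatment, and possibly its omission from the CRF.

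The count rests on exact name matching in the tables as extracted; a drug lost from one of the blank entries could only add to it. Whether any participant took one of these drugs, or whether CRF data were lost, cannot be known from the documents. The primary analysis, alpha and power are not affected.

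**What to change.** - Delete six entries from Appendix C: voriconazole, telithromycin and tacrolimus from the possible-QT row, thioridazine from the moderate-inducer row, procainamide from the MATE1/OCT2 row, and grapefruit juice from the moderate-inhibitor row.
- Add one sentence to Section 8.3, for example: *Any item or class prohibited in Appendix B, Section 8.4 or Section 4.1.1 remains prohibited even if it appears in Appendix C, subject only to the exceptions already stated (topical preparations; herbals or supplements approved by the PI).*
- Send sites a short memo naming the six items.

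The sentence in 8.3 does most of the work. It also covers the anticancer agents in Appendix C, which Appendix B, Section 8.4 and the note after 4.3.6 already bar as a class, and the herbal entry. The deletions help the reader who opens only Appendix C. The cost is a small text amendment and the memo, with no change to design, data collection or analysis.

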Appendix D: Concomitant Medications

In general, the use of any concomitant medication deemed necessary for the care of the patient is permitted in this study, except as specifically prohibited below. Combination administration of study drugs could result in drug-drug interactions (DDI) that could potentially lead to reduced activity or enhanced toxicity of the concomitant medication and/or ribociclib.

The following lists are not comprehensive and are only meant to be used as a guide. The lists are based on the Oncology Clinical Pharmacology Drug-Drug Interaction Database (release date: 29 Oct 2012), which was compiled from the Indiana University School of Medicine's P450 Drug Interaction Table (<http://medicine.iupui.edu/clinpharm/ddis/main-table/>) and supplemented with the FDA Draft Guidance for Industry, Drug Interaction Studies – Study Design, Data Analysis, and Implications for Dosing and Labeling (February 2012) (<http://www.fda.gov/downloads/drugs/guidancecomplianceregulatoryinformation/guidances/ucm292362.pdf>), and the University of Washington's Drug Interaction Database (<http://www.druginteractioninfo.org/>). For current lists of medications that may cause QT prolongation and/or torsades de pointes (TdP), refer to the CredibleMeds® website (<https://crediblemeds.org/>). Please contact the medical monitor or the PI with any questions.

Appendix E: Correlative Studies for the Feline Trial ([name])

While CDK4/6 inhibitors such as palbociclib have been approved by FDA for the use in combination with letrozole for the treatment of patients with ER+ breast cancer, at the present time, no response/predictive markers have been identified. Therefore, correlative studies will be performed to identify potential markers associated with the combination treatment of letrozole and LEE011. Four sets of correlative studies will be conducted. The objectives of these studies are:

- a) To determine whether treatment with letrozole and LEE011 will be affected by gene mutation in the cancer by Exome Sequencing of tumors.
- b) To perform RNA Sequencing and reverse phase protein array (RPPA) analyses to search for potential markers associated to the treatment outcome.
- c) To define potential markers, identified through our preclinical studies, related to the activity of letrozole and LEE011 by IHC.
- d) To determine whether miRNA and lncRNA in peripheral blood can be used as markers of the activity of letrozole and LEE011.

1. Exome sequencing

We will perform Exome Sequencing analysis on 40 tumor specimens (20 patients who have complete or very good partial response and 20 patients who had stable disease and or partial response) collected prior to treatment (diagnostic tumor biopsy specimens) to determine whether any somatic mutations in the tumors that affect the treatment outcome. Mutation status, allelic imbalance, and/or copy number variations of cancer-related genes (including, but not limited to: *RB1*, *CCND1*, *CDKN2A*, *CDK4*, *CDK6*, etc.) will be analyzed. Note that a gene will be considered as amplified if six (6) or greater copies of a given gene are present in the sample. Loss will be defined if zero (0) copies of a given gene are present in the sample. For this purpose, the results of this analysis will be correlated with clinical efficacy data. As these data are extensive and complex, only those markers that show at least 5% alteration frequency will be shown, as well as genes associated with the key pathway of interest.

2. RNA Sequencing and RPPA

As non-biased approaches, RNA Sequencing and RPPA will be performed on fresh frozen specimens collected before and six months after treatment of letrozole + LEE011 (36 pairs). These analyses will provide gene and protein expression signatures in the collected tissue. Expression changes before and after treatment will be correlated to the response of the combination treatment. In tumor tissue samples, an evaluation of the expression of genes/proteins related to the mechanism of action of CDK4/6, Rb pathway, cell cycle pathways or downstream effects, and cancer pathobiology may be evaluated (for example, loss of *CDKN2A* and/or *RB1*, amplification of *CCND1*, *FOXM1*; Cyclin B etc.) to assess any potential correlation with response to LEE011.

3. Immunohistochemical analysis

Pretreatment formalin-fixed paraffin-embedded tumor tissue should be in a whole block or unstained slides. Tissue will also be obtained following completion of study drugs (breast-conserving surgery or mastectomy) or at the time of progression (core biopsy). Tumor specimens submitted as a FFPE tissue block will be returned to the sites by end of study or upon request. Tumor samples will be analyzed by IHC of proteins associated with response or resistance to LEE011 therapy. IHC markers, e.g. pRB and PTEN, will be listed by marker and

treatment group and summarized using summary statistics (mean, standard deviation, median, minimum, maximum).

4. Peripheral blood

Blood will be collected prior to treatment, at discovery of disease progression or at end of treatment, whichever occurs first. In addition, paraffin blocks of formalin-fixed diagnostic tumor biopsy specimens before treatment will be requested from each patient.

Gene expression profile analysis will be performed to determine how LEE011 + letrozole treatment affects gene expression, including aromatase. The processing of the tumor for gene expression profiling of the samples will be carried out at the Wash U TPC or City of Hope Functional Genomics core facility. These facilities have experienced laboratories for expression profiling that are highly automated and that have extensive quality control procedures. Processing the samples will ensure consistent sample handling and high quality gene expression data. Collection of tumor samples for expression profiling is an important part of this study and whenever possible should be collected at the time points indicated below.

Exome Sequencing and Gene Expression Profiling of Tumor Samples

Molecular studies of clinical samples obtained from patients with cancer can provide rich clinical and biological information. For example, gene expression profiling of diagnostic breast cancer samples has been used to identify expression profiles associated with risk of metastasis (van de Veer et al., 2002; van de Vijver et al., 2002). In this protocol, pretreatment and on-treatment samples of tumor (in patients with accessible tumor) will be collected for correlative molecular studies. These samples will be used to search for (1) somatic gene mutations that affect the response to letrozole + LEE011, (2) gene expression profiles that predict response to letrozole + LEE011 and (3) expression changes that occur after exposure to letrozole + LEE011. In addition, off-treatment samples will be requested. These samples will be used to search for gene expression changes that occur after acquired resistance to letrozole + LEE011. The samples will also be used for confirmatory studies based on the gene expression results. Results from these gene expression studies may provide important information regarding the mechanisms of response and the mechanisms of resistance to letrozole + LEE011. Ultimately, these results could guide the selection of patients for treatment with letrozole + LEE011 and guide strategies for preventing or overcoming resistance to these drugs. In addition, paraffin blocks of formalin-fixed diagnostic tumor biopsy specimens will be requested from each patient. If more recent paraffin blocks of tumor biopsy specimens from the same patient are available, these will also be requested. These blocks will be used to identify molecular markers that are associated with response to letrozole + LEE011.

Appendix F: Drug Compliance Assessment Tool (Sample Participant Pill Diary)

Investigator Initiated Trial Protocol: CLEE011XUS10T
The Feline Trial - PRINCIPAL INVESTIGATOR - [name]

PARTICIPANT PILL DIARY for CONTINUOUS DOSING Ribociclib/Placebo + Letrozole

Participant Study
Number

AT THE SAME TIME EACH DAY
For each dose take with a large glass of water (8 ounces)
or regular (not Seville) orange juice (**No** grapefruit):

Cycle Number

400 mg of Ribociclib/Placebo
2.5 mg of Letrozole

Please write the date, amount taken and any comments.

	Date	Amount Taken		Comments
		Ribociclib/Placebo	Letrozole	
EXAMPLE:	6/1/2009	2	1	Hot flashes an hour later
Day 1				
Day 2				
Day 3				
Day 4				
Day 5				
Day 6				
Day 7				
Day 8				
Day 9				
Day 10				
Day 11				

Continued on Next Page
Page 1 of 2

Pill Diary 400mg_Version 10-Jun-2016

Investigator Initiated Trial Protocol: CLEE011XUS10T
The Feline Trial - PRINCIPAL INVESTIGATOR - [name]

THE UNIVERSITY OF KANSAS
CANCER CENTER

Participant Study Number _____

Cycle Number _____

		Amount Taken		Comments
		Ribociclib/Placebo	Letrozole	
EXAMPLE:	6/1/2009	2	1	Hot flashes an hour later
Day 12				
Day 13				
Day 14				
Day 15				
Day 16				
Day 17				
Day 18				
Day 19				
Day 20				
Day 21				
Day 22				
Day 23				
Day 24				
Day 25				
Day 26				
Day 27				
Day 28				

Investigator Initiated Trial Protocol: CLEE011XUS10T
The Feline Trial - PRINCIPAL INVESTIGATOR - [name]

THE UNIVERSITY OF KANSAS
CANCER CENTER

PARTICIPANT PILL DIARY for INTERMITTENT DOSING

Ribociclib/Placebo + Letrozole

Participant Study Number

AT THE SAME TIME EACH DAY

For each dose take with a large glass of water (8 ounces) or regular (not Seville) orange juice (**No** grapefruit):

Cycle Number

600 mg of Ribociclib/Placebo

2.5 mg of Letrozole

Please write the date, amount taken and any comments.

	Date	Amount Taken		Comments
		Ribociclib/Placebo	Letrozole	
EXAMPLE:	6/1/2009	3	1	Hot flashes an hour later
Day 1				
Day 2				
Day 3				
Day 4				
Day 5				
Day 6				
Day 7				
Day 8				
Day 9				
Day 10				
Day 11				

Continued on Next Page

Page 1 of 2

Pill Diary 600mg_Version 10-Jun-2016

Investigator Initiated Trial Protocol: CLEE011XUS10T
The Feline Trial - PRINCIPAL INVESTIGATOR - [name]

THE UNIVERSITY OF KANSAS
CANCER CENTER

Participant Study Number _____

Cycle Number _____

	Date	Amount Taken		Comments
		Ribociclib/Placebo	Letrozole	
EXAMPLE:	6/1/2009	3	1	Hot flashes an hour later
Day 12				
Day 13				
Day 14				
Day 15				
Day 16				
Day 17				
Day 18				
Day 19				
Day 20				
Day 21				
Day 22		DO NOT TAKE Ribociclib/Placebo		
Day 23		DO NOT TAKE Ribociclib/Placebo		
Day 24		DO NOT TAKE Ribociclib/Placebo		
Day 25		DO NOT TAKE Ribociclib/Placebo		
Day 26		DO NOT TAKE Ribociclib/Placebo		
Day 27		DO NOT TAKE Ribociclib/Placebo		
Day 28		DO NOT TAKE Ribociclib/Placebo
